1. INTRODUCTION

This Statistical Analysis Plan (SAP) describes the analyses for Part B of study DZ2019E0001, which is a phase 2 pivotal study. The statistical analyses required for part A of DZ2019E0001 were documented in a separate analysis plan.

The SAP contains a more technical and detailed elaboration of the analysis described in the Clinical Study Protocol (CSP). It also includes detailed procedures for executing the statistical analysis required.

The SAP was written based on the following documents:

Document	Version #	Date
Protocol	12.0	July 24, 2023
CRF	8.0	February 28, 2023
Memo for dropping dose	NA	July 27, 2023

2. OVERVIEW AND INVESTIGATIONAL PLAN

2.1 Study Objectives and Endpoints/Estimand

The objectives of part B of study DZ2019E0001 are listed as below.

2.1.1 Primary Objective and Estimand

Objectives	Endpoint/Estimand Description	
To evaluate anti-tumor activity of DZD9008 in advanced NSCLC patients with EGFR Exon20ins at defined dose(s) by assessment of Objective Response Rate (ORR)	Endpoint: Objective Response Rate (ORR) according to Response Evaluation Criteria in Solid Tumors (RECIST) version 1.1 evaluated by an Independent Review Committee (IRC), where confirmation of response is required.	
	Estimand Description:	
	Treatment: DZD9008 200 mg or 300 mg QD.	
	Population: Full Analysis Set (FAS) will be used for analysis, including all the NSCLC patients with documented EGFR Exon20ins mutations in tumor tissue, who were previously treated with platinumbased chemotherapy, received at least one dose of DZD9008, have at least one measurable lesion at baseline as identified by IRC.	
	Variable: Binary variable indicating whether patient is a responder who achieved confirmed complete response (CR) or partial response (PR) prior to progressive disease (PD), as evaluated by IRC according to RECIST 1.1;	

Objectives	Endpoint/Estimand Description	
	Intercurrent Event with Strategy:	
	PD evaluated by IRC	
	While on treatment strategy: the intercurrent event is already captured in the variable definition	
	Treatment Discontinuation due to reason other than PD evaluated by IRC	
	Treatment policy strategy: Intercurrent event is ignored, tumor response data irrespective of treatment discontinuation are considered in analysis.	
	New Anticancer Therapy	
	While on treatment strategy: Only the tumor response data prior to start of the new anticancer therapy are of interest.	
	Population-level Summary: Confirmed ORR, which is defined as the proportion of responders.	

2.1.2 Secondary Objectives and Endpoints

Objectives	Endpoint/Variable	
To assess anti-tumor efficacy of DZD9008 using additional endpoints	DoR, Progression Free Survival (PFS), DCR and BOR and % of Change in Size of tumor lesion according to RECIST 1.1 using assessments performed by an IRC	
	ORR, DoR, PFS, DCR, and BOR and % of Change in Size of tumor lesion using investigators assessments according to RECIST 1.1	
	Description of OS	
To determine the safety and	AEs/SAEs	
tolerability of DZD9008	Laboratory data	
	Vital signs	
	Physical examination	
	ECG	
	Echocardiogram/MUGA	
	Pulmonary function test	
To characterize the PK of DZD9008	Plasma DZD9008 and metabolite concentration and derived PK parameters if deemed appropriately	

2.1.3 Exploratory Objectives and Endpoints

The analysis of exploratory endpoints below will also be included in this SAP.

- To explore the impact of DZD9008 treatment and disease state on health state utility by using EQ-5D-5L health state utility index based on patient reported data.
- To assess AEs of DZD9008 by using subjects reported specific CTCAE symptoms (PRO-CTCAE) and FACIT GP5 questionnaire.
- To investigate the effect of DZD9008 on proof-of-mechanism (PoM) biomarkers in tumor biopsy, e.g., EGFR phosphorylation (pEGFR)

The EQ-5D-5L, PRO-CTCAE and FACIT GP5 are collectively called patient-reported outcome (PRO) data.

2.2 Overall Study Design

DZ2019E0001 is a phase I/II, open-label, multicenter study of DZD9008 administered orally in patients with advanced stage NSCLC with EGFR or HER2 mutation. There are two parts in this study: Part A and Part B (dose extension).

Cohorts for dose escalation, dose expansion and food effect will be included in part A of the study.

Part B is a phase 2, open-label, randomized pivotal study with 2 dose arms to evaluate the anti-tumor efficacy of DZD9008 in previously treated NSCLC patients with EGFR Exon20ins mutation. Simon two-stage design [1] will be used within each dose arm respectively. When both dose arms pass stage 1, the response rate of two arms will be compared using stage 1 data to identify the more effective arm .

It's anticipated to enrol approximately 103 NSCLC patients with EGFR Exon20ins into each arm. Each patient who signed informed consent form will undergo screening during the 28 days prior to first dosing to confirm eligibility. Patient passed screening will be randomized at ratio of 1:1 to receive DZD9008 300 mg or 200 mg once daily with food until disease progression. RECIST 1.1 assessments are scheduled from Cycle 3 Day 1 (± 7 days) and then every 6 weeks (± 7 days). Patients who discontinue DZD9008 for reasons other than progression will continue RECIST 1.1 assessments as scheduled until objective disease progression. A discontinuation visit may be performed after drug discontinuation to collect the data required, and a safety follow up will be conducted 28 days following the discontinuation of DZD9008. Following disease progression, the patient, patient's family, or the patient's current physician must be contacted every 6 weeks for survival information up to the time of the final OS analysis. The detailed schedule of events for part B of study can be found in Appendix A.

The earliest data cut-off for the primary analysis of ORR may take place 3 months after the last patient enrolled, to allow all patients to complete two follow-up RECIST assessments. At this time, DoR and safety/tolerability will also be summarized. The Clinical Study Report (CSR) of primary analysis may include, but not limited to, ORR, DoR, safety and tolerability data.

The full CSR of Part B will report the analysis of all primary and secondary endpoints (including updated ORR and DoR, DCR, tumor shrinkage, PFS and OS). The data cut-off for this analysis will take place approximately 8 months after the last patient is enrolled to ensure that the last responder could be followed up for at least 6 months after initial documented response. All patients will continue to be followed up for an updated analysis based on cut-off that will occur between 12 - 24 months after the last patient is enrolled. All endpoints will be updated and summarized in an addendum to the CSR.

2.3 Randomization

Eligible patients will be stratified by the brain metastasis at baseline (Yes, No) and number of regimens of prior anti-cancer systemic therapy (<3, 3) and randomized to the DZD9008 200 mg QD or 300 mg QD at the ratio of 1:1.

2.4 Determination of Sample Size

In Part B, patients will be randomized into one of the two dose arms. Each dose arm uses a Simon two-stage design.

Bonferroni method is employed to control the family-wise type I error. The analysis in two arms will be performed independently, at one-sided significance level of 0.0125.

The primary endpoint will be ORR by IRC. Under a Simon two-stage design, a sample size of 103 within each arm is required to test a null hypothesis of ORR at one-sided significance level of 0.0125, with expected ORR of 0.3 and the null hypothesis refers to real world data of 2nd line chemotherapy for NSCLC patients with EGFR Exon20ins [2-3].

In the first stage, patients will be enrolled in each arm. If the number of responses is less than or equal to out of patients in the first stage then the arm will be stopped. If the arm proceeds to the second stage, additional patients will be enrolled to reach a total of 103 patients. If or more responses are observed, then the null hypothesis is rejected in this arm.

3. ANALYSIS SET

The analysis of data will be based on different subsets according to the purpose of the analysis, which are also called analysis sets. The definitions of the analysis sets applicable for part B of study are provided in this section.

3.1 All Patients

All patients screened (who signed informed consent form) will be included in this analysis set. It's mainly used for the individual data listing, and also the overall summary of screen failures.

3.2 All Randomized Patients

All patients randomized will be included in this analysis set.

Note: This analysis set will not be used for analysis directly considering that randomization is not applicable for all patients enrolled in part B. But the data for the randomized patients in safety analysis set and full analysis set will be presented following the principle in Section 5.1.

3.3 Safety Analysis Set (SS)

All patients who received at least 1 dose of DZD9008 will be included in the Safety Analysis Set.

SS is the primary analysis set for safety data. And the safety analysis will be performed according to the actual treatment received by each patient, including the erroneously treated patients (e.g., those assigned to receive dose A who actually received dose B, those who failed to meet the selection criteria). If there is dose modification (such as dose reduction or shift from 200 mg to 300 mg), the initial actual dose taken by the patient during the treatment period will be regarded as actual treatment for analysis.

3.4 Full Analysis Set (FAS)

The Full Analysis Set (FAS) will consist of all NSCLC patients with documented EGFR Exon20ins mutations in tumor tissue, who were previously treated with platinum-based chemotherapy, received at least 1 dose of DZD9008 and have measurable disease at baseline as identified by IRC. The mutation in tumor tissue (resection, biopsy, pleural effusion pellet processed in formalin-fixed paraffin-embedded block, etc.) will be determined based on the clinical trial assay. The patients wrongly reported as EGFR Exon20ins mutations by local lab will be excluded from FAS, such as the complex mutation

FAS is the primary set for efficacy analysis. Patients will be analyzed according to their initially assigned dose level in FAS.

To support the development and approval of companion diagnosis devices, two additional analysis sets were defined in CSP as subset of FAS:

Centrally Confirmed EGFR Exon20ins by Tumor Tissue Analysis Set

All patients in FAS with EGFR Exon20ins mutation confirmed in tumor tissue by central laboratory.

• Centrally Confirmed EGFR Exon20ins by Plasma ctDNA Analysis Set

All patients in FAS with EGFR Exon20ins mutation confirmed in plasma ctDNA by central laboratory.

3.5 Pharmacokinetics Set (PKS)

All dosed patients who has at least one measurable plasma concentration of DZD9008 post dose with no protocol deviations or AE thought to impact the analysis of the PK data.

The statistical analysis of PK data will be performed based on the PKS.

3.6 Paired Biopsy Set (PoM cohort)

All dosed patients with a pre-study tumor biopsy and one tumor biopsy on study treatment will be included in the paired biopsy set.

4. ENDPOINTS DEFINITION AND DERIVATION

4.1 Extent of Exposure

Extent of exposure to DZD9008 will be checked for all treated patients based on the variables below:

Treatment duration (months): calculated as (last dose date of DZD9008 during treatment period – first dose date of DZD9008 during treatment period + 1)/30.4375;

If the treatment is ongoing (any status other than permanently discontinued) for the patient at the cut-off for analysis, the last dose date can be imputed as the cut-off date. If the first/last dose date is missing/partial after imputation for cut-off, the treatment duration cannot be calculated and will be reported as missing.

- Cumulative dose (mg): the sum of actual doses administered during treatment period;
- Actual Dose Intensity (ADI) (mg/day): calculated as cumulative dose (mg)/total planned days of exposure (day), where total planned days of exposure in part B of study is equal to the treatment duration in days;

• Relative Dose Intensity (RDI) (%): Actual dose intensity /planned dose intensity*100%, where planned dose intensity is defined as the daily dose assigned at the beginning of study.

Patients with at least one dose reduction and patients with at least one dose interruption during the whole exposure period before 'Drug Permanently Discontinued' was recorded will be identified for analysis purpose.

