In Part A dose expansion cohorts 3 - 6, patients are recommended to take DZD9008 with a low-fat meal. The low-fat meal is defined as approximately 400 to 500 Kcal with about 25% of calories comes from 11 - 14 grams of fat. Meal record will be collected at clinic site on PK sampling days as described in Table 7. Compliance with prandial conditions for non-PK sampling days is to be confirmed by the study personnel during the study visits (e.g., through patient diaries).

In Part B, patients will receive repeat daily dosing of DZD9008 at 200 mg and 300 mg with food to further investigate its anti-tumor efficacy, safety/tolerability and PK.

Following review and approval from IEC/IRB and/or local regulatory authority (as applicable) on the optimal RP2D selection (i.e., dropping the suboptimal dose), patient who is under screening will start treatment at optimal dose level. Patient who has been enrolled in optimal RP2D cohort can stay and maintain the pre-defined treatment course. The ongoing patient who has been randomized to another (suboptimal) Part B dose cohort can maintain the same dose level, or shift to receive the optimal dose if (a) judged by the investigator that it is of the best clinical benefit to patient; (b) patient's re-consent is obtained.

Dose should be taken approximately 24 hours apart at the same time point each day. On PK and plasma ctDNA sampling day, the dose should be instructed to take by site personnel. Doses should not be missed. If a subject misses taking a scheduled dose, within a window of 12 hours, it is acceptable to take the dose. If it is more than 12 hours after the dose time, the missed dose should not be taken and should be recorded, and subjects should be instructed to take the dose at the next scheduled time. If a subject vomits after taking their DZD9008, they should not make up for this dose.

Enrollment of patients into Part A dose expansion cohort 5 will be triggered when emerging data shows DoR reaches 6 months.

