5.5 Extent of Exposure

The extent of exposure data will be listed and summarized by treatment group in the safety set. If 10% or higher difference in number of patients is observed between analysis sets, the tables can be repeated in other analysis sets (e.g., FAS).

The descriptive statistics will be provided for treatment duration, the number and percentage of patients with treatment duration in the following categories will also be reported:

- <3 months;
- 3-<6 months;
- 6-<9 months;
- 9-<12 months;
- > 12 months.

The cumulative dose, ADI and RDI during treatment period will be summarized descriptively in the safety analysis set. A categorical summary of RDI (<80%, 80-100%, >100%) will also be performed.

Number and percentage of patients with at least one dose reduction or treatment interruption will be reported, respectively.

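### For patients who move from 200 mg to 300 mg, relative dose intensity is still divided by the starting dose, so for them it no longer measures the share of planned drug taken

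*SAP*

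**What the plan says.** SAP 4.1 builds RDI in three steps.

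- Cumulative dose is "the sum of actual doses administered during treatment period".
- Actual dose intensity (ADI) divides that by days of exposure, and "total planned days of exposure in part B of study is equal to the treatment duration in days".
- RDI divides ADI by planned dose intensity, where "planned dose intensity is defined as the daily dose assigned at the beginning of study".

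The dose can change upward by design. Under Protocol 5.1, once the optimal dose is agreed, an ongoing patient in the other Part B cohort "can maintain the same dose level, or shift to receive the optimal dose", subject to the investigator's judgement and re-consent. Protocol 5.1.4 repeats this. SAP 3.3 lists among dose modifications events "such as dose reduction or shift from 200 mg to 300 mg" and keeps such patients in the group of their initial dose. SAP 1 cites a memo on dropping a dose, dated July 27, 2023.

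SAP 5.5 summarises RDI by treatment group in the safety set, and adds: "A categorical summary of RDI (<80%, 80-100%, >100%) will also be performed". Neither document resets the RDI denominator, or splits exposure, when a patient shifts.

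**The concern.** RDI is usually read as the share of planned drug that was taken. Dividing by the starting dose serves that purpose while doses can only stay the same or fall. Here the plan itself raises the assigned dose for some patients. After the shift the mg taken rise by half while the reference stays at 200 mg/day, so the ratio mixes dose escalation with dose delivery.

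What is at stake is the 200 mg column of the RDI summary. Shifted patients stay in that column, the error only goes upward, and there is no matching error in the 300 mg column. A between-dose comparison of RDI would therefore favour 200 mg to the extent that patients shifted. Individual patients can also fall in a category that misstates how much of their planned drug they took.

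**Working it through.** The documents give no RDI figure to reproduce, so the SAP 4.1 formula is applied directly.

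**Inputs**

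- Starting dose 200 mg/day, dose after the shift 300 mg/day (SAP 3.3).
- RDI denominator 200 mg/day throughout (SAP 4.1).
- f, the share of treatment time before the shift: not in the documents, varied from 0 to 1.
- c, the share of planned doses taken: assumed for illustration.

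**Formulas**

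- ADI = c × [200f + 300(1 - f)], if doses are missed evenly.
- RDI under the SAP = ADI / 200.
- RDI against the dose planned on each day = ADI / [200f + 300(1 - f)] = c.
- Ratio of the two = [200f + 300(1 - f)] / 200 = 1 + 0.5(1 - f).

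**Full compliance (c = 1, time-weighted RDI 100%)**

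| f | ADI, mg/day | RDI under the SAP |
|---|---|---|
| 0.90 | 210 | 105% |
| 0.75 | 225 | 112.5% |
| 0.50 | 250 | 125% |
| 0.25 | 275 | 137.5% |
| 0.10 | 290 | 145% |
| towards 0 | towards 300 | towards 150% |

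**30% of doses missed throughout (c = 0.7, time-weighted RDI 70%, category <80%)**

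| f | RDI under the SAP | Category reported |
|---|---|---|
| 0.75 | 0.7 × 112.5% = 78.75% | <80% (unchanged) |
| 0.50 | 0.7 × 125% = 87.5% | 80-100% |
| 0.25 | 0.7 × 137.5% = 96.25% | 80-100% |
| 0.10 | 0.7 × 145% = 101.5% | >100% |

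**20% missed throughout (c = 0.8).** The time-weighted RDI is 80%, already in the 80-100% category. The SAP gives 90% at f = 0.75, 100% at f = 0.5 and 110% at f = 0.25. Only the last changes category, so a milder shortfall often stays where it belongs.

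**Reduction to 200 mg right after the shift, no other missed doses.** Table 3 of the protocol puts 200 mg one level below 300 mg. ADI is 200 mg/day at any f, so the SAP reports exactly 100%. The time-weighted RDI is 200 / [200f + 300(1 - f)]: 80.0% at f = 0.5, 72.7% at f = 0.25 and 69.0% at f = 0.10. RDI cannot show that reduction.

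**Patients not affected.** For 200 mg starters who do not shift, and for 300 mg starters, the denominator is the planned dose. A 300 mg starter reduced to 200 mg for half the time scores (0.5 × 300 + 0.5 × 200) / 300 = 83.3%, which is correct.

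**The case against.** The best defence is that this is a stated convention, in line with the rest of the SAP. Section 3.3 groups patients by initial dose, section 4.1 uses the same anchor, and RDI then means intensity relative to the starting dose. The >100% category shows that high values were expected. Protocol 5.1.5 bars going back up after a reduction for a drug-related event, so the optimal-dose shift is the main planned route into that category, and many shifted patients will be visible there.

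The consistency is real, but it does not restore the meaning of the ratio. Someone cut back to 200 mg straight after shifting scores 100% and looks like a fully compliant 200 mg patient. The >100% category flags some shifted patients without correcting their values, and it misses those whose shortfall pulls them below 100%.

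A second defence stands. A reader might infer that missed and reduced doses are hidden in the trial's reporting generally. The documents do not support that. SAP 5.5 counts patients with at least one reduction or interruption and summarises cumulative dose and ADI in mg/day. SAP 5.7.1 tabulates adverse events leading to interruption and to reduction. Protocol 7.9.2 lists dose modifications. None of these uses the RDI denominator, so the masking is confined to RDI.

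**Conclusion.** The point holds for 200 mg patients who shift to 300 mg, and only for them. Their RDI is multiplied by 1 + 0.5(1 - f) and can cross a SAP 5.5 category boundary.

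Three larger claims should not be drawn from this.

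- That RDI is inflated by 50%. A factor of 1.5 is a limit that needs a shift at about the first dose, whereas only patients already ongoing can shift. At mid-exposure the factor is 1.25.
- That mean RDI in the 200 mg group is inflated by some stated amount. This depends on how many shift and when, and the documents give neither. Shifting is optional and needs re-consent.
- That the efficacy conclusion is affected. RDI enters no test, endpoint or dose-selection rule, and the response-rate analysis does not use it.

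This is a minor flaw in a descriptive exposure summary. The illustrations assume even or immediate changes in dosing; the multiplying factor itself follows from the definitions alone.

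**What to change.** In SAP 4.1, define planned cumulative dose as the sum over treatment days of the daily dose assigned under the plan, updated at an optimal-RP2D shift and left unchanged for toxicity reductions. Then RDI = cumulative dose / planned cumulative dose × 100%. A fully compliant shifted patient scores 100% whenever the shift occurs, and later reductions or missed doses show. The alternative is to keep the present denominator up to the shift and report RDI separately before and after it.

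The cost is one sentence and a little programming. Protocol 7.9.2 already calls for dosing dates, doses and modifications, so no new collection should be needed. The CRF is not among the documents, so confirm that it separates an optimal-dose shift from other dose changes. The 200 mg group's RDI will look less favourable if any patients shifted. It would help to state how many shifted and the median time to shift beside the table.

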4.2 Efficacy Endpoints

The tumor assessment will be performed by the IRC and investigators independently in this study, following RECIST version 1.1. The efficacy endpoints related to RECIST assessment will be derived based on the evaluation by IRC and investigators respectively, following the rules in subsections below. More details for IRC assessment are documented in the independent review charter.

4.2.1 Primary Efficacy Endpoint

The primary efficacy endpoint is ORR according to RECIST 1.1 assessed by IRC, where confirmation of response is required.

ORR is defined as the percentage of patients who have best overall response (BOR) of Complete Response (CR) or Partial Response (PR) prior to any evidence of progression (as evaluated by IRC based on RECIST 1.1). Any CR or PR which occur after a further anticancer therapy is received will not be included in numerator of the ORR calculation, where further anticancer therapy (also called as new anticancer therapy) includes the systematic anticancer therapy or definitive radiothrapy received for the study indication after first dose of DZD9008.

In part B of study, RECIST assessments will be performed by IRC and investigator independently, from Cycle 3 Day 1 (\pm 7 days) and then every 6 weeks (\pm 7 days). A visit overall response of CR is defined when all Target Lesion (TL) and Non-Target Lesion (NTL) lesions present at baseline have disappeared (with the exception of lymph nodes which must have short axis < 10 mm to be considered non-pathological) and no new lesions have developed since baseline. A visit response of PR is defined when the sum of diameters of the TLs has decreased by 30% or more compared to baseline (with no evidence of progression) and the NTLs are at least stable with no evidence of new lesions. More details regarding RECIST assessment can be found in the appendix F of CSP.

BOR is defined as the best response recorded from first dose of DZD9008 until RECIST progression is documented for each patient. BOR represents the best response that a patient has had prior to any subsequent cancer therapy received, irrespective of whether or not patients discontinued treatment of DZD9008. There are 5 potential categories for BOR (from best to worst): CR, PR, Stable Disease (SD), Progressive Disease (PD) and Not Evaluable (NE). When SD is believed to be the best response, at least 35 days from first dose (6 weeks minus 7-day visit window) is required.

When confirmation of CR/PR is required, BOR of CR or PR will only be claimed if a response of CR/PR is recorded by two visits with time interval of at least 4 weeks (28 days). For confirmed CR, one intervening response of NE are possible and are acceptable, but PD is not; For confirmed PR, one intervening response of NE or SD are possible and are acceptable, but PD is not. More examples for BOR derivation with confirmation required are provided in Table 1. Note the BOR variable provided by IRC will not be used for statistical analysis directly, as new anticancer therapy was not considered in the derivation rule by IRC.

BOR where confirmation of response is required or not will be derived and reported respectively. Eventually ORR will be calculated based on the BOR derived for each patient, as defined above.

Table 1 Derivation of BOR where confirmation is required

			1
Assessment x	Assessment x+1	Assessment x+2	BOR
Death			NE (for death before the first RECIST assessment)
CR	CR	CR/PD/NE	CR
CR	NE	CR	CR
PR	CR	CR	CR
PR	CR	PD/NE	PR
PR	PR	Any	PR
PR	SD/NE	PR	PR
CR	PR		Not allowed. Reappearance is progression
CR	PD/NE		SD*
PR	SD/PD/NE		SD*
SD/NE	CR	PD/NE	SD*
SD/NE	PR	SD/PD/NE	SD*
SD	PD		SD*
PD			PD
NE			NE
NE	PD		PD
NE	NE		NE

^{*} SD is believed to be the best overall response only if the minimum time requirement (5 weeks from baseline) for SD is met.

